2 STUDY DESCRIPTION

2.1 Schedule of Analyses

Phase 1 (escalation cohort) has previously been analyzed; the original SAP is attached as an appendix to this document. This SAP applies similar methodology to Phase 2 (expansion cohort), the following analyses of which are planned:

Table 1: Planned Analyses of Expansion Cohort

Meeting/Format	Timing	Purpose
DMC Interim #1	When the first 6 subjects in the ulocuplumab 1000mg arm have had opportunity for 28 days of follow-up	Review of all available safety data, especially pertaining to the ulocuplumab 1000mg dose; results will be available for review by BMS also
DMC Interim #2	When around 60 subjects (20 per treatment arm) have completed 2 months of treatment and follow-up	See DMC Charter for additional details; results will be available for review by BMS also
DMC Interim #3 (SAE only)	About 12 months after interim #2	See DMC Charter for additional details
Final analysis	After all patients have had opportunity for 6 months of follow-up	For final report (CSR)
DMC final meeting	When 100% of subjects have completed or discontinued from all study drugs	Review all safety data for the proposed treatment regimen and provide insight for potential future trials
Study completion analysis	At completion of study (subject follow-up complete)	Review mature OS data

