Based on data from CA212016 escalation phase data and nonclinical toxicology studies of ulocuplumab, there is a possibility of hematologic toxicity. Intensive safety monitoring is included in CA212016 to allow investigators to recognize toxicities that may be related to ulocuplumab or to the potentiating of chemotherapy-associated toxicities. The protocol contained inclusion and exclusion criteria appropriate to the population, instructions for screening tests, AE monitoring and dose modification guidelines. AEs and SAEs were reviewed on an ongoing basis by the BMS Medical Monitor to look for and identify significant trends and safety issues at the earliest point.

Because there was a single Grade 3 infusion-related reaction in a DLBCL subject in CA212001, if a subject experiences a Grade 2 infusion reaction with ulocuplumab, the subject is required to receive prophylactic premedication for subsequent infusions of ulocuplumab. The pre-medications included, but not limited to, diphenhydramine, acetaminophen, and low-dose corticosteroids, which pose minimal risk to subjects in the dose and frequency given. If a subject experiences a Grade ≥ 3 infusion reaction, the subject discontinued the study treatment. Therefore, the overall risk/benefit assessment did not change.

Based on preliminary clinical experience with another CXCR4-targeted agent, non-clinical studies of ulocuplumab that indicate anti-tumor activity in AML models, and the acceptable clinical safety profile and preliminary efficacy data for AML subjects observed in CA212001 and CA212016 to date, ulocuplumab in combination with chemotherapy may be a promising therapeutic approach for further investigation and its potential benefits appear to outweigh any potential risks.

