6.1 Serious Adverse Events

A *Serious Adverse Event (SAE)* is any untoward medical occurrence that at any dose:

- results in death
- is life-threatening (defined as an event in which the subject was at risk of death at the time of the event; it does not refer to an event which hypothetically might have caused death if it were more severe)
- requires inpatient hospitalization or causes prolongation of existing hospitalization (see **NOTE** below)
- results in persistent or significant disability/incapacity
- is a congenital anomaly/birth defect
- is an important medical event (defined as a medical event(s) that may not be immediately life-threatening or result in death or hospitalization but, based upon appropriate medical and scientific judgment, may jeopardize the subject or may require intervention [eg, medical, surgical] to prevent one of the other serious outcomes listed in the definition above. Examples of such events include, but are not limited to, intensive treatment in an emergency room or at home for allergic bronchospasm; blood dyscrasias or convulsions that do not result in hospitalization.) Potential drug induced liver injury (DILI) is also considered an important medical event. (See [Section 6.6](#) for the definition of potential DILI.)

Suspected transmission of an infectious agent (eg, pathogenic or nonpathogenic) via the study drug is an SAE.

Although pregnancy, overdose, cancer, and potential drug induced liver injury (DILI) are not always serious by regulatory definition, these events must be handled as SAEs. (See [Section 6.1.1](#) for reporting pregnancies).

Any component of a study endpoint that is considered related to study therapy (eg, death is an endpoint, if death occurred due to anaphylaxis, anaphylaxis must be reported) should be reported as SAE (see Section 6.1.1 for reporting details).

NOTE:

The following hospitalizations are not considered SAEs in BMS clinical studies:

- a visit to the emergency room or other hospital department < 24 hours, that does not result in admission (unless considered an important medical or life-threatening event)
- elective surgery, planned prior to signing consent
- admissions as per protocol for a planned medical/surgical procedure
- routine health assessment requiring admission for baseline/trending of health status (eg, routine colonoscopy)

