7 DATA MONITORING COMMITTEE AND OTHER EXTERNAL COMMITTEES

An independent data monitoring committee (DMC) will be constituted for review of safety information and assessment of overall benefit/risk balance in this study. Specific data to be reviewed and timing of the reviews by the DMC will be described in a DMC Charter.

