7 STATISTICAL ANALYSES

7.1 General Methods

Unless otherwise specified, the following are analyses of the expansion cohort, by treatment group, and will be produced for both DMC interim #2 and final analyses. A subset of these analyses will support DMC interim #1 and DMC interim #3 (SAE); further details will be given in the DPP and DMC Charter.

In general, continuous variables will be summarized using descriptive statistics, i.e. mean, standard deviation, median, minimum and maximum values. Geometric mean and coefficient of variation will also be presented for sample serum concentration-time data and PK parameters. Categorical variables will be summarized by frequencies and percentages. Percentages will be rounded and may not always add up to 100.

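### The last scheduled DMC review before dosing ends is SAE-only, so non-serious DLTs, cytopenias, safety ECGs and AE discontinuations after Interim #2 reach the DMC only afterwards, unless the Charter adds them

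*SAP*

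**What the plan says.** SAP section 2.1, Table 1 schedules four DMC reviews of the expansion cohort.

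- **Interim #1:** all available safety data, once the first 6 subjects at 1000 mg have had the chance of 28 days of follow-up.
- **Interim #2:** "When around 60 subjects (20 per treatment arm) have completed 2 months of treatment and follow-up".
- **Interim #3:** labelled "DMC Interim #3 (SAE only"), timed "About 12 months after interim #2", with further detail left to the DMC Charter.
- **Final DMC meeting:** "When 100% of subjects have completed or discontinued from all study drugs". This meeting covers all safety data.

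SAP 7.1 assigns the full set of section 7 outputs to Interim #2 and the final analysis. For the other interims it says: "A subset of these analyses will support DMC interim #1 and DMC interim #3 (SAE"). It defers details to the data presentation plan and the Charter.

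Protocol section 7 gives the DMC the task of "review of safety information and assessment of overall benefit/risk balance in this study", and also leaves the specific data and timing to the Charter.

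**The concern.** The protocol's own safety triggers do not depend on seriousness. Protocol 5.3.1 defines DLTs by grade, duration and attribution. Protocol 4.6.1.1 and Table 4.6.1.2-1 require discontinuation for prolonged marrow suppression, a grade 3 or higher infusion reaction, or a confirmed QTcF of 500 msec or more. Any of these can occur without meeting the SAE definition. Stopping a drug because of an AE is not an SAE criterion either.

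Protocol 1.5, drawing on the escalation data and nonclinical toxicology, says "there is a possibility of hematologic toxicity". Much of that signal would sit in laboratory grades and in non-serious AEs.

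A committee asked to judge overall benefit and risk would, at its last scheduled look while subjects can still be on drug, hold only the serious part of the risk side. The rest would arrive when it could inform later trials but no longer protect subjects in this one.

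**Working it through.** **1. The plan's own figure.** The documents give no figure for DMC coverage. The only sizing figure is the precision of the remission rate with 40 per arm. It reproduces: the exact 95% interval is 0.433 to 0.751 for 24/40 (stated 0.43-0.75) and 0.293 to 0.615 for 18/40 (stated 0.29-0.62). It does not bear on this point beyond confirming 40 per arm.

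**2. What the DMC is scheduled to see, and when** (SAP Table 1 and 7.1)

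| Review | Data | Subjects possibly on drug? |
|---|---|---|
| Interim #2 | Full section 7 outputs | Yes |
| Interim #3 | SAEs | Yes |
| Final meeting | All safety data | No |

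The final analysis for the study report is a separate row and is not listed as a DMC review.

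**3. What an SAE-only package carries**

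| Item | Basis of definition | In an SAE package? |
|---|---|---|
| Non-hematologic DLT (Protocol 5.3.1) | Related, grade 3 or higher, Cycle 1 | Only if serious |
| Hematologic DLT (Protocol 5.3.1) | Related, grade 4 for more than 14 days, or marrow not recovered within 8 weeks | Only if serious |
| Laboratory grades (SAP 7.6.6) | CTCAE grade | Only where an associated event is serious |
| ECG intervals (SAP 7.6.7) | Measured value | Only where an associated event is serious |
| AE discontinuation (SAP 7.6.3) | Action taken | Only if the AE is serious |

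**4. Subjects affected.** Planned total is 120, at 40 per arm. The Interim #2 trigger is about 60, at 20 per arm.

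- Beyond the trigger: 120 - 60 = 60 subjects (50%), or 40 - 20 = 20 per arm.
- On ulocuplumab: 2 x 20 = 40.

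This is an upper bound. SAP 6.2 and 6.3 summarize safety in all treated subjects, so subjects who start treatment while the 60 complete their 2 months could also appear in the Interim #2 tables.

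**5. Events that come too late for Interim #2 even in the first 60.** Two months is about 61 days.

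- Marrow non-recovery is judged 8 weeks after the last study drug. If the last dose is Cycle 1 Day 15, that is 15 + 56 = Day 71. A subject with only the minimum follow-up cannot yet have met it.
- LDAC-alone subjects without remission may add ulocuplumab only after 4 cycles: 4 x 28 = 112 days. That exposure falls after Interim #2 except in subjects enrolled early enough. Addition after a relapse has no such minimum.

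**6. Chance that something relevant is missed.** The documents give no rate for non-serious relevant events, so the rate p is an assumption. P(at least one) = 1 - (1 - p)^n.

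| p | n = 20 (one arm) | n = 40 (ulocuplumab) |
|---|---|---|
| 2% | 0.33 | 0.55 |
| 5% | 0.64 | 0.87 |
| 10% | 0.88 | 0.99 |
| 20% | 0.99 | >0.99 |

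For DLTs alone, the expected number not shown is 40 x DLT rate x share non-serious. With an assumed rate of 10% to 20% and 25% to 75% non-serious, this runs from 40 x 0.10 x 0.25 = 1 to 40 x 0.20 x 0.75 = 6.

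**The case against.** The strongest objection is that the Charter and the data presentation plan are not available, and both documents defer to them. Extra data or ad hoc reviews cannot be excluded. This makes the conclusion conditional but does not remove it. The SAP states the limit in two places that agree, so a broader Charter would itself need reconciling with the SAP.

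A second objection is that other safeguards exist. The study is open-label, possible DLTs are discussed with the sponsor's medical monitor, individual discontinuation criteria apply, and Protocol 1.5 describes ongoing medical monitor review of AEs (in the past tense). The final analysis is tied to 6 months of follow-up, not to the end of dosing. These narrow the gap, but none is independent DMC review.

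A third is that a lighter third look, after two broader ones, is a legitimate choice in an exploratory, non-comparative study. That is fair, and no rule in the documents is broken. The point is a mismatch between the committee's remit and the data scheduled for it.

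Several stronger readings are tempting but not supported:

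- *All grade 3-4 cytopenias are left out.* Protocol 6.1 names blood dyscrasias without hospitalization as possible important medical events, and a life-threatening event is an SAE. Only those judged non-serious are missed.
- *More than half of the 1000 mg arm is unseen.* Table 1 expects 20 per arm at Interim #2, which is half of 40. Neither the length of the pause nor any catch-up is given.
- *Events that are not toxicity distort the review.* The protocol does say "Although pregnancy, overdose, cancer, and potential drug induced liver injury (DILI) are not always serious by regulatory definition, these events must be handled as SAEs", and SAEs are collected whatever their cause. But SAP 7.6.2 plans a separate table of drug-related SAEs, and no stated rule at Interim #3 turns on an SAE count.
- *The serial ECG data are missed.* Serial recordings fall on Cycle 1 Day 1 and Cycle 2 Day 15, with a minimum of 15 subjects per dose level. Much of that minimum may already be in Interim #2, so the gap is mainly in routine safety ECGs.

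**Conclusion.** The point holds in a limited form. As the SAP stands, the DMC's last scheduled review before all dosing ends shows SAEs only. Non-serious DLTs, non-serious grade 3-4 cytopenias and other laboratory grades, routine safety ECGs and non-serious AE discontinuations arising after the Interim #2 data cut are deferred to the final meeting. They are delayed, not lost.

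The deferral affects up to about 60 of 120 subjects, later cycles of the earlier subjects, and most ulocuplumab added in the LDAC-alone arm. It rests on three conditions: the Charter does not widen the package, the Interim #2 tables do not already cover many subjects beyond the trigger, and some relevant events are classed as non-serious. The accrual rate is not given, so the number still on drug at Interim #3 is unknown. For the same reason, the documents do not support replacing the planned calendar timing with a subject-count trigger.

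**What to change.** In SAP Table 1 and SAP 7.1, replace the SAE-only scope of Interim #3 with the safety outputs already planned for Interim #2, by arm:

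- deaths with primary reason;
- all AEs and drug-related AEs by grade;
- SAEs;
- AEs leading to discontinuation;
- laboratory grades;
- ECG summaries.

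Add a DLT count by arm, because SAP 7.6 lists no DLT table for the expansion cohort. Make the Charter say the same. Keep the planned timing of about 12 months after Interim #2.

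The cost is a fuller data cut with the cleaning it needs, one rerun of existing tables, and one new DLT table. No extra meeting is needed, and no dose or clinical rule changes.

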2.2 Study Design

A total number of 6 (Phase 1) plus up to approximately 120 (Phase 2), i.e. 126 subjects overall, will be treated in this study. The entire study is expected to last approximately 7 years, with the addition of the expansion cohort and overall survival (OS) follow up.

Cohorts

Phase 1: an open-label escalation cohort of 6 subjects with AML to assess the safety and tolerability of ulocuplumab.

Phase 2: an exploratory, non-comparative open-label expansion cohort of up to approximately an additional 120 AML subjects, randomized in a 1:1:1 manner to the following treatment arms:

- 1) ulocuplumab 800 mg in combination with LDAC 20 mg BID;
- 2) ulocuplumab 1000 mg in combination with LDAC 20 mg BID;
- 3) LDAC 20 mg BID alone.

Randomization will be suspended in the ulocuplumab 1000 mg + LDAC arm while safety data from the first 6 subjects in this arm are evaluated for DLTs (as part of DMC Interim #1). DLTs and all other toxicities are defined and evaluated using the National Cancer Institute Common Terminology Criteria for Adverse Events Version 4.03 (NCI CTCAE v4.03). DLTs are defined based upon events considered to be related to ulocuplumab in combination with LDAC and that occurred during the first cycle of drug administration (28 days). Randomization to the

ulocuplumab 1000 mg + LDAC arm will resume if $\leq 33\%$ of subjects experience a DLT. If $> 33\%$ of subjects are observed with DLTs, this treatment arm will not accrue additional subjects.

[figure not shown]
Study Periods

The study consists of the following 3 periods:

- Screening: the 28 days following initiation of screening assessments and before administration of the first dose of any study drug, during which subjects are evaluated for study eligibility.
- Treatment: subjects will receive LDAC on Days 1-10 of each 28-day cycle. In addition, subjects randomized to arms 1 and 2 will be administered ulocuplumab on Days 1 and 15 (also on Day 8, in cycles 1-2). Subjects who are tolerating study treatment, clinically stable and not progressing rapidly at the end of each cycle may continue with additional cycles until disease progression, development of unacceptable toxicity, intercurrent illness preventing treatment, or patient request or investigator decision to stop treatment. Delay of subsequent cycles for recovery from myelosuppression (or other AE) is allowed at investigator discretion.
 - Note: for the LDAC alone arm, ulocuplumab 800 mg may be added on Days 1 and 8 (also on Day 15, in cycles 1-2) if a subject does not achieve CR or CRi confirmed by blast count reduction after 4 treatment cycles or if they relapse after achieving complete remission.
- Follow-up: a follow-up visit will be completed 30 (± 7) days from the last dose of study therapy. Subjects will continue to be followed every 3 months for ongoing drug-related AEs until they have resolved, returned to baseline or are deemed irreversible, or until loss to follow-up or withdrawal of study consent. Subjects will also be followed every 3 months for OS for up to two years, until death, loss to follow-up or withdrawal of study consent.

The study design schematic is presented in Figure 1. Further details of the study design may be found in [Section 3.1](#) of the Protocol.

Figure 1: Study Design Schematic

2.3 Treatment Assignment

After informed consent has been obtained and the subject’s initial eligibility is established, the subject is assigned a subject number in IWRS. Following completion of all screening evaluations, site personnel will make a call to the IWRS, which will randomly assign Phase 2 subjects in a 1:1:1 manner to one of the 3 treatment arms (as described in [Section 2.2](#)). Randomization to the ulocuplumab 1000 mg + LDAC arm will be suspended while the safety of the first 6 subjects on this dose is assessed (see Section 2.2). Note that randomization will continue in the other 2 arms during this review. (Therefore, expected total numbers randomized are approximate.)

2.4 Blinding and Unblinding

The study is open-label.

Unblinded reports of interim data will be available to the DMC, without the use of fully- or partially-blinded treatment codes. Treatment codes will be provided by the BMS randomization coordinator to the reporting statistician after the database lock for the DMC analyses. Interim results for this exploratory study (for which there will be no inferential testing between treatment groups) will be available for review by a limited number of BMS personnel for planning purposes. Protocol Amendments

There are currently 7 amendments. The history of protocol amendments is summarized in the table below.

Table 2: Protocol Amendments

Amendment	Date	Main changes
1	24 Oct 2014	Clarifications in response to the PMDA review for Clinical Trial Notification
2	7 May 2015	Removal of restriction on AML (newly diagnosed, elderly); modification of prior therapy-related criteria and hepatitis B and C infection criteria
3	2 Nov 2016	Addition of randomized expansion cohort, with primary objective to assess preliminary efficacy; clarification of Phase 2 secondary objectives (safety and tolerability, overall remission [OR], CR/CRi, duration of remission [DoR], OS); added exploratory objectives (receptor occupancy [RO] and biomarkers)
4 (Brazil only)	19 Jan 2017	Clarification of post-study access to therapy in Brazil
5	10 Feb 2017	Addition of central laboratory cytogenetic testing; clarification of dosing and study assessment details
6	29 Mar 2017	Clarification of Phase 2 design (as exploratory, non-comparative; primary analysis to be conducted after all patients had opportunity for 6 months of follow-up; clarified that DoR will be censored on the date of last relapse-related assessment prior to the initiation of alternative anti-cancer therapy); increased local laboratory window allowances for hematology, chemistry and urinalysis to 72 hours; clarification of dose modifications and dose delays; clarification of study design; addition of whole exome sequencing to bone marrow and peripheral blood biomarker testing; added ECG, biomarker, cytogenetic and molecular analysis sections.
7	27 Jul 2017	Revision of exclusion criteria to specify allogeneic transplants in patients who received prior hematopoietic stem cell transplantation; clarification of hematology sampling schedule during cycles 1 and 2; revision of peripheral

		blood and serum/plasma collection criteria during end-of-study treatment and follow-up assessments.
--	--	---

3 OBJECTIVES

See original SAP in the appendix for Phase 1 (escalation cohort) objectives. Below are shown the Phase 2 (escalation cohort) objectives.

3.1 Primary

- To estimate preliminary efficacy in terms of complete remission (CR/CRi = CR + CRi) in subjects treated at two different dose levels of ulocuplumab, 800 mg and 1000 mg, in combination with LDAC

3.2 Secondary

- To characterize the immunogenicity of ulocuplumab
- To characterize the PK profiles of ulocuplumab in combination with LDAC
- To evaluate the effects of ulocuplumab on ECG intervals, including QTc intervals

- To assess OS in subjects treated with ulocuplumab 800 mg or 1000 mg in combination with LDAC
- To assess the safety and tolerability of ulocuplumab in subjects with AML treated with ulocuplumab at two different dose levels 800 mg and 1000 mg in combination with LDAC
- To assess rates of OR (= PR + CR + CRi) as well as duration of complete remission (CR/CRi) in subjects treated with ulocuplumab at two different dose levels 800 mg and 1000 mg in combination with LDAC
- To assess efficacy (in terms of rates of CR/CRi and OR and DoR, respectively, in subjects treated with LDAC alone, to compare with historical controls of LDAC in the same patient population. Overall survival will also be assessed in this group.

[REDACTED]

4 ENDPOINTS

This section summarizes Phase 2 (expansion cohort) efficacy, safety and other endpoints.

4.1 Efficacy Endpoints

4.1.1 Primary Endpoint

- Rate of complete remission (CR/CRi), prior to the initiation of any alternative therapy (including any subsequent ulocuplumab 800 mg for subjects in the LDAC alone arm). Response will be assessed by the investigator in accordance with the 2003 International Working Group (IWG) response criteria. The primary analysis will be conducted after all patients have had opportunity for 6 months of follow-up.

4.1.2 Secondary Endpoints

- Rate of OR (= PR + CR + CRi)
- DoR: the time from the date of first documented CR/CRi to the date of death or relapse. For subjects who remain alive and have not relapsed following remission, DoR will be censored on the date of last relapse-related assessment prior to the initiation of alternative anti-cancer therapy.
- OS: the time between the first date of treatment and the date of death due to any cause. A subject who has not died will be censored at the last known alive date.

